Population and patient selection criteria

A cohort of 100 adults (18-75 years) patients with UC, either naïve or under standard of care (both responders and non-responders to therapies) will be prospectively enrolled. In all cases, the Montreal classification, and the clinical and endoscopic indexes of activity will be carefully assessed. The control group consists of 100 sex- and age-matched subjects, selected in the same Center, undergoing colonoscopy as examination in the diagnostic algorithm for lower abdominal symptoms and **that results normal, thus confirming the diagnosis of** irritable bowel syndrome, and who were not taking drugs possibly affecting immune response and microbiota composition. **A small cohort of patients (n=20) suffering from microscopic colitis will be also enrolled as pathological control group.** All enrolled patients and controls will undergo lower endoscopy with mucosal sampling as **diagnostic** workup for their condition. Patients with active UC undergo colonoscopy and laboratory tests according to international

guidelines and depending on physician judgement. More in depth, active UC patients will undergo colonoscopy at baseline, while laboratory tests will be performed at baseline, and at 3 and 6 months. As optional follow-up, accordingly with physician evaluation, some patients will undergo medical examination and laboratory tests at 9 and 12 months, and colonoscopy at 12 months. The aim of the study is settled at 6 months, but adding the optional follow-up at 9 and 12 months, will aid us to understand if patients with EBV colitis undergo colectomy more frequently than patients without EBV colitis. Patients with UC in remission will undergo colonoscopy and laboratory tests according to ECCO-ESGAR guidelines [52]. Patients with suspicion of irritable bowel syndrome will undergo colonoscopy and laboratory tests if alarm features are present (aged >45-50 years, anemia, weight loss, familiar history of colon cancer, blood mixed in the stool). The exclusion criteria include: significant comorbidities, malignancy, pregnancy, organ failure, immunodeficiencies, active infections, recent abdominal surgery, or invalidating psychiatric-neurological disorders.

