5.2.2 Secondary endpoint

a- Comparison of the presence of EBV infection in the cohort of patients suffering from UC and divided into the following subgroups: a) new diagnosis; b) responders to conventional therapies; c) non-responders to conventional therapies, in order to unravel whether it is a bystander or causative of the onset/relapse of the disease and whether it is responsible for refractoriness to standard of care.

b- Evaluation of the diagnostic ability in detection of EBV infection of ISH performed on mucosal specimens with respect to qRealTime-PCR.

c- Evaluation of the diagnostic ability in detection of EBV infection between qRealTime-PCR performed on peripheral blood samples with respect to mucosal specimens.

d- Evaluation of association between mucosal/blood viral load and mucosal damage as endoscopically assessed (see paragraph 5).

e- Evaluation of association between clinical index of UC activity and EBV infection.

f- Evaluation of association between steroid therapy (absent, previous or current) and EBV infection.

g- Evaluation of association between immunosuppressive therapy (absent, previous or current) and EBV infection.

h- Evaluation of association between biological therapy (absent, previous or current) and EBV infection.

i- Evaluation of the prognostic role of EBV infection on the 6 and 12 months outcome (colectomy / number of hospitalization / cause of hospitalization).

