The **control group consists of 100 sex- and age-matched subjects**, selected in the same Center, undergoing colonoscopy with mucosal sampling as diagnostic workup for IBS in order to exclude macroscopic or microscopic disorders, or because alarm features are present: aged > 45-50 years, anemia, family history of colon cancer. That are confirmed to be suffering from IBS (C1), functional constipation/diarrhea (C2, C3) and functional abdominal bloating/distension (C4), following the Rome IV criteria (48), and who were not taking drugs possibly affecting immune response (steroids, immunosuppressant and biological agents) and microbiota composition (antibiotics, probiotics, prebiotics, proton pump inhibitors).

In addition, a small cohort of patients (n=20) suffering from **microscopic colitis** will be also enrolled as pathological control group (49).

All enrolled patients and controls undergo lower endoscopy with mucosal sampling and laboratory tests as diagnostic workup for their condition:

- Patients with active UC undergo colonoscopy and laboratory tests according to International guidelines and depending on physician judgement: active UC patients will undergo colonoscopy at baseline and laboratory tests at baseline, and at 3 and 6 months. A number of these patients, according to medical judgment, undergo medical examination at 9 and 12 months, and laboratory tests and colonoscopy at 12 months as optional follow-up. This is why the aim of the study is calculated at 6 months, but adding the optional follow-up at 9 and 12 months, will aid to understand if patients with superimposed EBV colitis undergo colectomy more frequently than patients without EBV colitis
- Patients with UC in remission undergo colonoscopy and laboratory tests as standard follow-up of their pathological condition according ECCO-ESGAR guidelines [52] (ex: to evaluate mucosal healing or screening)
- Patients with IBS undergo colonoscopy and laboratory tests only if alarm features are present (age > 45-50 years, anemia, family history of colon cancer, weight loss, blood mixed with stool).

Each enrolled case will undergo clinical and/or laboratory examination as standard follow-up of his/her pathological condition. All the laboratory tests are shown in the Appendix 5.

Each patient and control give written informed consent after approval by the local Bio-Ethics Committee is obtained.

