8.2 Analysis

Data will be described with the mean and standard deviation or the median and 25th-75th percentiles if continuous and as counts and percent if categorical. For the primary endpoint we will compute the prevalence as the ratio of the number of patients diagnosed with EBV infection to the number of patients evaluated, together with its 95%CI. We will use the Fisher exact test to compare the prevalence in UC patients to that of control. We will report the mean difference in proportions and its 95%CI. We will use binomial regression models with identity link (command binreg in Stata), to adjust for potential confounders, such as, but not limited to, age, gender, duration of disease and treatment. We will apply the 1:10 rule to adapt the number of confounders evaluated to the sample size. We will compare the prevalence of EBV infection between UC subgroups with the Fisher exact test (EP2a). In these cases, given in particular that the ratio of responders to non-responders is at yet unknown, we will compute *a posteriori* the power for the comparison. We will compute

sensitivity, specificity, area under the ROC curve and predictive values with 95% CIs for EP2b and EP2c. We will use the Spearman R and the Fisher exact test to assess the association, for continuous and categorical independent variables, respectively, with the dependent variables of EP2d to EP2h. All estimates will be presented with their 95% CI.

We will use Cox regression to assess the association of EBV infection with colectomy and of hospitalization for any cause; we will use Poisson regression to assess the association of EBV infection with the number of hospitalization from any cause. For secondary endpoints assessing associations, we will also fit regression models to adjust for possible confounders (as for the EP1) and report adjusted mean differences in proportions and 95% CI. We may also use propensity score inverse probability weights to account for the bias by indication when assessing treatment effect on the outcome.

The exploratory endpoints will be only descriptive.

We will use Stata 17 or later versions for computations. A 2-sided p-value <0.05 will be considered statistically significant. We will apply the Bonferroni correction for post-hoc comparisons.

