9 WITHDRAWAL OF SUBJECTS

It is under the responsibility of the Principal Investigator in each IG-IBD Centre who has in charge the patient to withdraw her/him from the study and to advise both the Study Coordinator and Data Manager specifying the reason/s. The impossibility to harvest mucosal biopsies is considered a criterion for subject withdrawal. In this case, the patient's data will be removed from the database, but considered when assessing patient disposition. The development of malignancy or death are primarily considered as evolution of the underlying disease. In addition, a patient has the right to withdraw from the study at any time for any reason. Subjects who withdraw their consent are considered withdrawn from the study. The Principal Investigator has the right to terminate participation of any patient if it is deemed in the patient's best interest and if she/he develops severe psychiatric or neurological disorders. The reason and circumstances for premature discontinuation must be reported in the patient's electronic case report form (eCRF). This means that a patient may be withdrawn in every phase of the trial, from the inclusion to any time of the follow-up period. In summary, reasons of withdrawal include, but are not limited, to the following:

- Patient's decision,
- Withdrawal of patient consent to participate in the study,
- Physician's decision based on patient's well-being.

For any subject discontinuing the study the Principal Investigator should before do the following:

- Complete the eCRF, indicating in the final visit, the date of termination and the reason for discontinuing the study as well as the protocol deviation section, with all data not corresponding to a formal visit filled in the Early Termination visit.

In patients who do not come back for the scheduled study visits, documented efforts should be performed to convince she/he to continue attending study visits and if unsuccessful, at least the exact reason(s) should be obtained for their discontinuation and any adverse event associated to it should be recorded.

The patient will be replaced if her/his mucosal specimens are not available for the full analyses.

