l) The Informed Consent Form will include a statement by which the patient allows the Sponsor's duly authorised personnel, the IEC, and the regulatory authorities to have direct access to source data which supports the data on the eCRF (e.g., patient's medical file, appointment books, original laboratory records, etc.). These personnel, bound by professional secrecy, will not disclose any personal identity or personal medical information.

m) Data collection and study report form monitoring. All data obtained for this study will be entered into a regulation compliant Data Management System. Data will be recorded with an Electronic Data Capture system using eCRFs. Specifically, the Electronic Data Capture system will be based on the IGIBDReg platform. IGIBDReg is a novel workflow methodology and software tool that expedites the electronic collection of research data from a single site or multi-site clinical research study. The study database will be resident on OVH server (<https://www.ovhcloud.com/>) as required by European Certification

n) Procedure to account for missing or spurious data. In case of missing clinical assessment at follow-up visit, the last observation carried forward from the latest earlier visit will apply, while in case of missing clinical, endoscopic and histologic data by month 12, the evaluation of outcome will not be possible. We expect to have 10% patients on drop-out. IGIBDReg provides section to recording missing or N/A information.

o) Procedure to account for protocol deviations. Generally, a protocol deviation is not imperative for patient withdrawal. Before the statistical analysis begins, the protocol deviations must be taken into account for the analysis. The mandatory withdrawal reasons will be considered as major protocol deviations. Other protocol deviation will be classified as minor protocol deviation. Additionally, the lack of compliance with any of the inclusion/exclusion criterion, either identified before or after enrolment into the study, will be considered as major protocol deviation. Any protocol deviation must be recorded in the eCRF (specific section in IGIBDReg). Once the study has begun, any modification of the protocol deviation will be specified in the statistical analysis plan. This will be done before closing the database.

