14 PUBLICATION POLICY

After completion of the study, the Study Coordinator will prepare a draft manuscript containing final results of the study on the basis of the statistical analysis. The manuscript will be derived to the co-authors for comments and after revision will be sent to the appropriately selected peer-reviewed scientific journal. All information concerning this study has to be treated confidentially. In all publication/s the confidentiality of patients’ data will be ensured.

All publications, abstracts, presentations, manuscripts and slides including data from the present study will be submitted to and reviewed by the Study Coordinator for coordination and homogeneity purposes. By signing this study protocol, the investigators accept that the results of this study can be presented to national and international authorities. They also accept that in this context their name, address, qualification and grade of involvement in the trial will be published.

The Study Coordinator will be the Senior Author and the Corresponding Author of the relevant publication/s. The Authors’ list will include all the investigators (up to the maximum required by the Journal to whom the article will be submitted) in a decreasing order of patients included into the final analysis for the primary outcome, as well as the study statistician.

The funding body will be acknowledged within the publication/s, but they do not have any review and publication right on the data from the study, including their timelines for doing so.

It is responsibility of the Study Coordinator to notify the Principal Investigators of the outcome of the study by provision of the publication/s.

15 Study time table (Gantt chart)

The whole study duration is 36 months, while the time frame from the enrolment of the first patient is 32 months. The patients’ participation consists of a 3 weeks screening period, one week to undergo endoscopy with mucosal sampling and peripheral blood harvest, a 6 months mandatory follow-up period, a 6 further months of facultative follow-up period, and a 4 weeks end of study visit. Thus, the recruitment period lasts 29 months and the minimum expected duration of subject participation is of 7 months. The whole study duration is 36 months, and the subdivision of the activities by trimesters and by involved units is represented here below:

Task	I	II	III	IV	V	VI	VII	VIII	IX	X	XI	XII
1a												
1b												

Protocol code: REBUC
Effective date: 03/10/2022

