Annex 2: eCRF

Annex 3: Budget REBUC

Annex 4: Lista Centri REBUC

Appendix 1

SCCAI: Simple Clinical Colitis Activity Index

Variabile	Punteggio				
	0	1	2	3	4
Numero di scariche diurne	1 - 3	4 - 6	7 - 9	>9	
Numero di scariche notturne		1 - 3	4 - 6		
Urgenza di defecare		di corsa	immediatamente	incontinenza	
Presenza di sangue nelle feci	assente	tracce	occasionale	sempre	
Valutazione clinica globale	molto bene	lievemente al di sotto della normalità	scadente	pessima	terribile
Manifestazioni extraintestinali (1 punto per ciascuna manifestazione)					
Score totale					

Appendix 2

UCEIS: Ulcerative Colitis Endoscopic Index of Severity

Variabile	Punteggio				
	1	2	3	4	5
Pattern vascolare	normale		perdita a chiazze		obliterato
Eritema mucosale	assente		lievemente arrossata		molto arrossata
Superficie mucosale	normale		granulare		nodulare
Edema mucosale	assente		probabile		definito
Presenza di muco-pus	assente		poco		tanto
Presenza di sangue	assente	mucosale	luminale lieve	luminale moderato	luminale severo
Fragilità mucosale	assente	lieve	moderata	severa	molto severa
Fragilità mucosale al contatto	assente		probabile		definita
Presenza di erosioni-ulcere	assenti	presenza di erosioni	presenza di ulcere superficiali	presenza di ulcere profonde	
Estensione di erosioni-ulcere	assente	limitata	sostanziale	estesa	
Score totale					

Appendix 3

Schedule assessments in active UC

	Screening	Baseline	Mandatory follow-up		Optional follow-up	
			3 months	6 months	9 months	12 months
Clinical assessment	X		X	X	X	X
Body Mass Index		X	X	X	X	X
Diagnosis confirmation	X					
Clinical index of activity		X	X	X	X	X
Laboratory analyses		X	X	X		X
Blood sampling		X	X	X		X
Lower endoscopy		X				X
Endoscopic index of activity		X				X
Mucosal sampling		X				X
Histology examination		X				X
Immohistochemistry		X				X
ISH		X				X
Viral load assessment		X				X

Appendix 4

Schedule assessments in UC in remission and IBS

	Screening	Baseline
Clinical assessment	X	
Body Mass Index		X
Diagnosis confirmation	X	
Clinical index of activity		X
Laboratory analyses		X
Blood sampling		X
Lower endoscopy		X
Endoscopic index of activity		X
Mucosal sampling		X
Histology examination		X
Immunohistochemistry		X
ISH		X
Viral load assessment		X

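### The admission-count analysis names Poisson regression alone, with no person-time term and no allowance for overdispersion, although follow-up runs from 6 to 12 months

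*Protocol*

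**What the plan says.** **Model.** Protocol section 8.2: "we will use Poisson regression to assess the association of EBV infection with the number of hospitalization from any cause". Nothing is said about person-time, the variance estimator or the window over which admissions are counted.

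**Endpoint.** Section 5.2.2, item i: "Evaluation of the prognostic role of EBV infection on the 6 and 12 months outcome (colectomy / number of hospitalization", together with the cause of admission.

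**Length of follow-up.** Section 15 gives each patient "a 6 months mandatory follow-up period, a 6 further months of facultative follow-up period". Section 6, on active UC, says: "A number of these patients, according to medical judgment, undergo medical examination at 9 and 12 months". The Summary agrees: "As optional follow-up, accordingly with physician evaluation, some patients will undergo medical examination and laboratory tests at 9 and 12 months". Appendix 4, titled "Schedule assessments in UC in remission and IBS", lists only screening and baseline. Under section 9, "a patient may be withdrawn in every phase of the trial, from the inclusion to any time of the follow-up period".

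**Evaluability.** Section 10, item n: "in case of missing clinical, endoscopic and histologic data by month 12, the evaluation of outcome will not be possible". Section 6, by contrast, sets the study aim at 6 months and calls months 9 and 12 optional.

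**The concern.** Two features of the data do not sit well with an unqualified Poisson model.

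- **Dispersion.** Poisson regression with its default standard errors takes the variance to equal the mean. Section 6 deliberately mixes untreated, responding and refractory patients, and the sicker ones may be admitted more than once. Counts of that kind often vary more than the mean allows. The default interval is then too short and the test rejects too often.
- **Exposure.** A count grows with the time observed. Here that time ranges from 6 to 12 months, or less after withdrawal, and the treating physician decides who goes on. The Cox model named in the same sentence of section 8.2 handles unequal follow-up by censoring. A Poisson model does so only if exposure is entered.

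At stake is the prognostic statement on EBV and admissions, which is judged at a two-sided 0.05.

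**Working it through.** The protocol gives no admission rate, dispersion, rate ratio or power for this endpoint, so there is no figure of its own to reproduce. The numbers below show how large the effect is under stated assumptions.

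**Inputs from the protocol.** About 100 UC patients (8.1); 10% drop-out (10, item n), so 100 × 0.9 = 90; expected EBV prevalence 50% in non-responders and 10% in responders (8.1); two-sided 0.05 (8.2); 6 or 12 months observed (15).

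**Assumptions.** 30% EBV-positive, the midpoint of 10% and 50%, so 27 v 63 patients; 0.3, 0.5 or 1.0 admissions per year; gamma-Poisson counts with variance μ + kμ², k from 0 to 2; no true EBV effect; no covariates.

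**Step 1: overdispersion, with exposure handled correctly.** The default standard error is too small by a factor of about √(1 + kμ). With 9 months' mean follow-up, μ = 0.75 × yearly rate. For example, 0.5 per year with k=2 gives μ = 0.375 and √(1 + 2 × 0.375) = √1.75 = 1.32.

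Simulated type I error, 20,000 replicates per scenario. Ranges cover three splits of patients reaching 12 months (EBV-positive/EBV-negative): 50%/50%, 70%/30% and 100%/0%.

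| Admissions per year | k | √(1 + kμ) | Poisson, default variance, offset | Poisson, robust variance, offset |
|---|---|---|---|---|
| 0.3 | 0 | 1.00 | 3.2-3.9% | 3.8-4.4% |
| 0.3 | 1 | 1.11 | 5.3-5.7% | 4.3-4.7% |
| 0.3 | 2 | 1.20 | 7.8-7.9% | 5.0-5.2% |
| 0.5 | 0 | 1.00 | 4.1-4.4% | 4.9-5.2% |
| 0.5 | 1 | 1.17 | 8.8-9.0% | 5.8-6.0% |
| 0.5 | 2 | 1.32 | 12.4-13.6% | 6.3-6.8% |
| 1.0 | 0 | 1.00 | 4.8% | 5.3-5.7% |
| 1.0 | 1 | 1.32 | 13.1-14.0% | 5.8-6.2% |
| 1.0 | 2 | 1.58 | 21.4-22.1% | 7.2-7.5% |

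If everyone is counted over a common 6 months, means are smaller and so is the inflation. For k = 1 to 2 the default test rejects in 3.5-4.5% at 0.3 per year, 5.8-8.4% at 0.5 and 10.0-15.3% at 1.0.

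**Step 2: pooling 6- and 12-month counts with no exposure term.** If a share p of a group is seen for 12 months and the rest for 6, mean time is 0.5 + 0.5p years. Under no effect the expected rate ratio is the ratio of mean times:

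- 70% of EBV-positive v 40% of EBV-negative reach month 12: 0.85/0.70 = 1.21.
- 80% v 30%: 0.90/0.65 = 1.38.
- 50% v 50%: 0.75/0.75 = 1.00.

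For 70% v 40% without overdispersion, simulated type I error is 5.5%, 7.1%, 8.8% and 13.1% at 0.2, 0.3, 0.5 and 1.0 admissions per year.

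**Step 3: could follow-up length differ by EBV status?** Take section 8.1's prevalences and assume half the UC patients are non-responders. Per 100 patients there are then 50 × 0.5 + 50 × 0.1 = 25 + 5 = 30 EBV-positive, and non-responders make up 25/30 = 83% of them. Among the 70 EBV-negative they are 25/70 = 36%. If, as a further assumption, exactly the non-responders continue to month 12, the ratio is (0.5 + 0.5 × 0.833)/(0.5 + 0.5 × 0.357) = 0.917/0.679 = 1.35. Non-responder shares of 70% and 30% give 1.23 and 1.41.

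**The case against.** The strongest reply is that this argues from silence. An exposure term and a variance estimator are options within Poisson regression, and a protocol commonly leaves them to the statistical analysis plan, which is not at hand. A reader might infer that the sponsor will fit the model with default variance and no person-time, and that the intervals will therefore be too narrow. The documents do not say so. They also give no admission rate or dispersion, and at 0.3 per year with k=1 the default test is close to nominal. That part of the reply stands. What remains is that section 8.2 fixes the method by name and elsewhere goes down to the link function and the Stata command, so one more clause would fit its level of detail.

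A second reply is that endpoint i has fixed 6- and 12-month horizons, and that section 10 points towards excluding patients without month-12 data, not towards pooling unequal windows. A reader might also infer that a spurious rate ratio is built into the plan. It is not: that needs both pooling without exposure time and a link between EBV status and follow-up length. Step 3 makes such a link plausible, but no section states it. The fixed horizons do limit the problem. They do not remove it, because withdrawals shorten the 6-month window too, and the month-12 rule conflicts with month 12 being optional.

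Third, section 8.2 also plans confounder-adjusted models. Covariates such as treatment could absorb some of the extra variation, and the simulations are unadjusted. This may lower the figures, by an amount the documents do not allow one to estimate.

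**Conclusion.** The point holds as a conditional one. The analysis named for the number of admissions has no stated protection against overdispersion or unequal observation time, and the design makes both realistic.

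- If counts are overdispersed, type I error with a correct offset is about 5-6% at 0.3 admissions per year with k=1, 9-14% at 0.5 with k=1-2, and 13-22% at 1.0 with k=1-2. It is lower over a common 6-month window. With k=0 the intervals are not too narrow.
- If unequal windows are pooled without exposure time and EBV-positive patients are followed longer, the no-effect rate ratio is about 1.2 to 1.4. It is 1.00 if follow-up length is unrelated to EBV status.

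Admission rates, k and follow-up shares are all assumptions. One component of one secondary endpoint is affected; the primary endpoint and the sample size are not.

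**What to change.** In section 8.2, state that the number of admissions will be analysed over 0-6 months as the main window and 0-12 months as supportive. Use Poisson regression with robust variance, or negative binomial regression, with log observed follow-up time as offset. Say how observed time is defined for patients who withdraw and for UC patients in remission, whose schedule has no visit after baseline.

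Add two notes. First, the offset corrects for length of observation but does not remove informative selection into months 9 to 12, which is why the 12-month result should be supportive. Second, the month-12 evaluability rule in section 10, item n, must be reconciled with month 12 being optional in section 6, the Summary and Appendix 3.

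The cost is somewhat wider confidence intervals. In Stata the Poisson version needs two options, `exposure()` and `vce(robust)`. No extra patients or visits are needed, but the end-of-observation date must be available for each patient. Robust variance is not a complete cure at this sample size: in the table it still gives up to 7.5%, against 22.1% for the default.

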6 PATIENT SELECTION CRITERIA

For these purposes, a cohort of **100 patients with UC**, as diagnosed following the worldwide accepted criteria (2,41), either naïve or under standard of care (both responders and non-responders), will be prospectively enrolled. In all cases, the clinical and endoscopic indexes of activity will be carefully assessed. Specifically, to establish the refractoriness to current therapy, the following criteria will be applied: steroid-refractoriness is defined as the persistence of active disease despite an adequate dose and duration of steroid treatment (prednisone, 0.75–1 mg/kg day orally for at least two weeks; methylprednisolone, 1 mg/kg day intravenously for one week) (42); primary and secondary non-response to biological agents (infliximab, adalimumab, golimumab, vedolizumab) is considered as the lack of clinical improvement with induction therapy or recurrence of symptoms of disease activity during maintenance therapy despite an appropriate interval adjustment and dose escalation with exclusion of concomitant condition, respectively (43); resistance to immunosuppressive therapy (azathioprine, cyclosporine) on the basis of lack of clinical improvement after at least 4 weeks of treatment or the development of a flare of disease under appropriate maintenance dosage. For those patients following combination therapies, refractoriness is defined as the persistence of symptoms of active disease despite at least 4 weeks' treatment. In all cases, the Montreal classification is applied to assess the behavior, severity, and extent of the illness (44), while the clinical disease activity index is assessed according to the Simple Clinical Colitis Activity Index (SCCAI – Appendix 1) (45). Remission is defined as a SCCAI score of below 3 points. The endoscopic activity score is evaluated according to the Ulcerative Colitis Endoscopic Index of Severity (UCEIS – Appendix 2 - score ranging from 3 to 11, with a higher score indicating more severe disease) (46,47).

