- ❖ Quantitation of EBV and HCMV DNA. For each patient and control, the EBV and HCMV load will be assessed in terms of International Units (IU) on both freshly collected whole peripheral blood samples and endoscopic specimens harvested from colonic mucosa, by qRealTimePCR technique as previously reported (51). Specifically, in the IBD group, two snap-frozen biopsies will be taken from either inflamed and/or non-inflamed mucosa as assessed during the endoscopic examination, that is from the edge of the ulcers and the nearby damaged zones for the former and at least 20 cm away from the affected areas for the latter. Two snap-frozen biopsies from healthy mucosa (possibly transverse colon) will be collected from each non-IBD patient. Viral DNA extraction will be performed by using the EZ1 DNA Tissue kit and EZ1Virus Mini Kit v2.0 (Qiagen, Hilden, Germany), while EBV DNA will be quantified by using the artus EBV QS-RGQ PCR Kit (Qiagen), and HCMV DNA will be quantified by using the artus CMV QS-RGQ kit (Qiagen), according to the manufacturer's instructions. Results will be expressed as IU/ml of blood and IU/10⁵ cells. Normalization of viral DNA load in tissue samples will be obtained by quantitative determination of β_2 -microglobulin gene. The lower detection limit is 1 DNA input target DNA copies (51). This analysis will be carried out at the the Molecular Virology Unit in Pavia.

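### Section 8.2 fixes adjusted differences in proportions for all secondary association endpoints, but that measure does not fit EP2d and conflicts with the models named for EP2i

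*Protocol*

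**What the plan says.** Protocol Section 8.2 gives the primary endpoint (EP1) this adjusted analysis: "We will use binomial regression models with identity link (command binreg in Stata), to adjust for potential confounders". For the secondary association endpoints it then states: "we will also fit regression models to adjust for possible confounders (as for the EP1) and report adjusted mean differences in proportions". No endpoint is excepted.

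Section 5.2.2 defines EP2d as "Evaluation of association between mucosal/blood viral load and mucosal damage as endoscopically assessed". On the load side, Section 7.1 says "Results will be expressed as IU/ml of blood and IU/10⁵ cells". On the damage side, Section 6 describes the UCEIS as a "score ranging from 3 to 11, with a higher score indicating more severe disease". The unadjusted analysis of EP2d to EP2h is graded where the variable is graded: "We will use the Spearman R and the Fisher exact test to assess the association, for continuous and categorical independent variables, respectively".

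EP2e to EP2h have infection status as one of the two variables, for example "Evaluation of association between clinical index of UC activity and EBV infection". EP2i concerns colectomy and hospitalization at 6 and 12 months. Just before the sentence at issue, Section 8.2 assigns Cox regression to colectomy and any-cause hospitalization, and Poisson regression to the number of hospitalizations.

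**The concern.** A difference in proportions needs a yes/no outcome. EP2d has a quantity and a score, so the one adjusted estimate named for it cannot be produced without dichotomising something, and the protocol assigns no cut to this endpoint. The adjusted result would then no longer use the graded load that EP2d names, and it could depend on a cut chosen after the data are seen.

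This matters because Section 3 asks whether EBV causes tissue damage or only marks severe colitis. EP2d is the endpoint closest to that question, and an unadjusted Spearman coefficient cannot separate EBV from disease duration or treatment, both of which Section 8.2 lists as confounders.

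For EP2i, Cox and Poisson models yield hazard ratios and rate ratios. A plain difference in proportions would be on another scale and would treat a patient seen for 6 months like one seen for 12.

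**Working it through.** **Step 1. Fit of the measure, endpoint by endpoint.**

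| Endpoint | Outcome | Difference in proportions fits? |
|---|---|---|
| EP2a, EP2e to EP2h | EBV infection yes/no | Yes |
| EP2d | Load in IU, or endoscopic score | No |
| EP2i, colectomy and hospitalization | Time to event (Cox) | No; hazard ratio |
| EP2i, number of hospitalizations | Count (Poisson) | No; rate ratio |

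**Step 2. Is a cut available for EP2d?** Infection is defined in Sections 5.2.1 and 7.1 by detection of virus, so detectable versus undetectable exists. Section 3 mentions mucosal thresholds of 100 and 1000 copies. None of these is assigned to EP2d, none is given for blood, and they are in copies while results are in IU. No cut is given for the endoscopic score. Its range is also unsettled: Section 6 starts it at 3, but the ten items of Appendix 2 each start at 1, so the minimum there is 10 × 1 = 10.

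**Step 3. Follow-up for EP2i.** Section 6 and Appendix 3 make months 9 and 12 optional, and Section 10(n) expects 10% drop-out. Observation time will therefore differ between patients. Cox regression handles this by censoring, and a Poisson model can do so with an exposure term.

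**Step 4. What could dichotomising cost EP2d?** The protocol states no power for EP2d or EP2i. Its only power figures are for the primary comparison, and they reproduce: exact Fisher power with 100 per group against 1% is 76.86% at a prevalence of 10% (stated 76.9%) and 99.84% at 20% (stated 99.8%).

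Inputs for EP2d:
- n = 100 UC patients (Section 8.1); two-sided alpha 0.05 (Section 8.2).
- Detectable share p = 10% to 50%, the span of the expected prevalences in Section 8.1.
- Assumed: latent correlation r = 0.30 to 0.40 and one covariate.

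Model: latent load x standard normal; damage y = r·x + √(1 − r²)·e; observed load = x − c if x > c and 0 otherwise, with c = Φ⁻¹(1 − p). Least squares was used for the graded score, and a linear probability model stood in for the identity-link binomial. With 4,000 runs the simulation standard error is at most √(0.25/4000) = 0.8 points.

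Power at p = 30%:

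| r | Score kept, on load | Score cut (at half or top quarter), on load | Infection yes/no, on score |
|---|---|---|---|
| 0.30 | 60–62% | 42–44% | 63% |
| 0.35 | 75% | 54–56% | 77% |
| 0.40 | 86–87% | 68–69% | 88% |

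Unadjusted Spearman at r = 0.35 and p = 30%: 79%.

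Other detectable shares, compared with keeping the score:
- Cutting the score loses 11–20 points at p = 20% and 14–22 at p = 50%. The smallest losses arise at p = 10% with a top-quarter cut, where a rerun gave only 3–7 points.
- Modelling infection yes/no on the score gains at least about 5 points at p = 10–20% and loses 3–6 at p = 50%.

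**The case against.** The strongest reply has four parts.

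1. The regression is additional. Spearman remains the planned EP2d test and keeps the graded information. This stands, and it limits the point to supplementary analyses.
2. The reference to EP1 may carry over only the confounder set and the 1:10 rule, since the sentence speaks of regression models in general. A reader might infer that the binomial model is prescribed for every endpoint; the text does not settle that. The reported measure is fixed on either reading, so the mismatch remains.
3. The infection definition supplies a ready split, so a reader who infers that any dichotomy must be arbitrary goes too far. That split, however, turns EP2d into an infected/uninfected comparison and drops the load that the endpoint names.
4. Cox and Poisson models take covariates, and a competent analyst would report their ratios. That is likely. The models are not missing; the stated measure contradicts them.

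An SAP could repair this, but the protocol has not left the measure open. It has stated one that does not fit.

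**Conclusion.** The point holds as a misstated rule of minor weight. The adjusted measure in Section 8.2 is right for EP2a and EP2e to EP2h, fits neither variable of EP2d, and conflicts with the EP2i models. The primary endpoint, the sample size and the unadjusted secondary tests are unaffected.

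A reader might infer that EP2d loses about 20 points of power. The documents do not support that as a general figure. It appears when the score itself is cut, or when two fully continuous normal variables are assumed and one is split at its median. In the latter case, at r = 0.28 and n = 100, power is Φ(atanh(0.28)·√97 − 1.96) = 80.9%. With effective size 100 × 2/π it is Φ(atanh(0.28)·√60.7 − 1.96) = 61.1%, a gap of 19.8 points. The protocol's expected prevalences of 10% to 50% instead imply that 50% to 90% of patients have no detectable load. A detection split then costs at most about 6 points against the graded regression and may gain power; cutting the score costs roughly 6 to 22 points, less in the corner noted above. All these figures rest on assumed correlations, normal latent variables and a single covariate.

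**What to change.** Rewrite the sentence in Section 8.2 as three rules:

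- **EP2a, EP2e to EP2h:** adjusted differences in proportions with 95% CI, as for EP1.
- **EP2d:** an adjusted model that keeps both variables graded, for example ordinal or rank-based regression of the endoscopic score on load, for mucosa and blood separately, with undetectable loads kept at the lowest value and the same confounders. Report the coefficient with 95% CI.
- **EP2i:** adjusted hazard ratios from the Cox models and adjusted rate ratios from the Poisson model, each with 95% CI.

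One caution on EP2d. Adding an indicator for undetectable load and reporting the load slope alone would be a poor main result. The slope then rests only on patients with detectable load, about 100 × 0.30 = 30 at p = 30%, and its power is about 16% at r = 0.35 (roughly 13% to 21% for r = 0.30 to 0.40). If an indicator is used, test load and indicator jointly.

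The cost is one paragraph, with no new data and no extra patients. It should be settled before any outcome data are examined.
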